**CONFIDENTIAL**

Document Date: 29 Nov 2021

Page 22 of 34

ST-AD-008 version 05

## Statistical Analysis Plan

Sponsor Name: Golden Biotechnology Corporation

Sponsor Protocol ID: GH Covid-2-001

Covance Study ID: 000000203201

patients with more than one TEAE in a particular category are counted only once in that category:

- any AE;
- any AE by maximum severity (mild, moderate, severe);
- treatment-related AE;
- AE leading to study treatment discontinuation;
- AE leading to study discontinuation;
- AE leading to death;
- SAE;
- treatment-related SAE;
- treatment-related SAE leading to death;
- SAE leading to death;
- SAE leading to treatment discontinuation;
- SAE leading to study discontinuation.

The number and percentage of patients reporting each AE will be summarized by System Organ Class (SOC) and Preferred Term (PT) for the SS. SOC and PT will be sorted by descending frequency in Antroquinonol group. The following summaries will be produced:

- AEs, by SOC and PT;
- AEs by PT;
- AEs related to study treatment, by SOC and PT;
- AEs related to study treatment, by PT;
- AEs by maximum severity, by SOC and PT;
- AEs related to study treatment by maximum severity, by SOC and PT;
- AEs by highest relationship to study treatment, by SOC and PT;
- AEs causing discontinuation from study treatment, by SOC and PT;
- AEs related to study treatment causing discontinuation from study treatment, by SOC and PT;
- AEs causing discontinuation from study, by SOC and PT;
- SAEs, by SOC and PT;
- SAEs related to study treatment, by SOC and PT;
- AEs leading to death, by SOC and PT.

In the above summaries, patients with more than one AE within a particular SOC or PT are counted only once for that SOC or PT. For summaries by maximum severity, patients with multiple AEs within a particular SOC or PT will be counted under the category of their most severe AE within that SOC or PT. AEs with missing severity

## Statistical Analysis Plan

Sponsor Name: Golden Biotechnology Corporation  
Sponsor Protocol ID: GH Covid-2-001

Covance Study ID: 000000203201

will be included as severe in the overall count of patients with AEs, but will not be included in the counts of patients with AEs within a SOC or PT. For summaries by highest severity, patients with multiple AEs within a particular SOC or PT will be counted under the category of their highest relationship to study treatment within that SOC or PT.

No statistical comparisons of AEs between treatment groups will be performed.

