8.5. Safety Analysis

Safety variables include incidence of AEs (or TEAEs), laboratory test results, vital signs, and complete physical examination, ECG, and chest imaging (x-ray or CT scan) findings. All safety analyses will be based on the SS. No formal statistical analysis of the safety data will be performed.

Adverse events will be coded according to MedDRA, version 23.0 dated 19 April 2020 (exclusively meant for COVID-19) or later.

The number and percentage of patients with TEAEs, SAEs, TEAEs related to study treatment, SAEs related to study treatment, TEAEs leading to treatment discontinuation, TEAEs leading to study discontinuation, and TEAEs leading to death will be summarized by SOC, PT, and treatment group. In addition, the severity of TEAEs and relationship to study treatment will be summarized by SOC, PT, and treatment group.

The AE summary tables will include counts of patients. Therefore, if a patient experiences more than 1 episode of a particular AE, the patient will be counted only once for that event. If a patient has more than one AE that is coded to the same PT, the patient will be counted only once for that

PT. Similarly, if a patient has more than 1 AE within an SOC, the patient will be counted only once in that SOC.

Test values and change from baseline will be summarized descriptively for specific laboratory test results, vital signs, complete physical examination results, ECG findings, and chest imaging (x-ray or CT scan) findings. Where applicable, shift tabulations by treatment group will be presented.

Pregnancy test results and patients with confirmed positive pregnancy test result will be listed.

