## Statistical Analysis Plan

Sponsor Name: Golden Biotechnology Corporation  
 Sponsor Protocol ID: GH Covid-2-001

Covance Study ID: 000000203201

Principle	Value
Treatment group labels and order	Antroquinonol 100 mg BID Placebo
Tables	Data in summary tables presented by treatment group, assessment and visit (where applicable).
Listings	All data collected presented by treatment group, country, site, Patient, assessment and visit (where applicable), unless otherwise specified.
Descriptive summary statistics for continuous variables	Number of patients/observations (n), mean, standard deviation (SD), median, minimum (Min) and maximum (Max).
Descriptive summary statistics for categorical variables	Frequency counts and percentages [n (%)]
Denominator and for percentages	Number of patients in the analysis population, unless stated otherwise in table shell(s).
Precision for percentages	1 decimal place
Include "Missing" as category	Yes, when the number missing is greater than zero for at least one treatment group.
Display to one more decimal place than collected value	For efficacy and safety: Mean Mean Difference Median
Display to two more decimal places than collected value	For efficacy and safety: Standard Error Standard Deviation Confidence Interval
Display to three significant figures	For PK: Mean Standard Deviation Geometric Mean Median Min Max
Limit of precision for displays	4 decimal places
Date Format	DDMMYYYY

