### 7.7.2 Adverse Events

All adverse events (AEs) recorded on the eCRF will be coded using the MedDRA dictionary [Version 23.0 dated 19 Apr 2020 or a later version if updated during the study (exclusively meant for COVID-19)] and classified as either pre-treatment AEs or treatment – emergent AEs (TEAEs) as follows:

- Pre-treatment AEs are events that start after the signing the informed consent form and prior to the date of first dose of study treatment.
- TEAEs are events with start date on or after the date of first dose of study treatment and up to 2 weeks after date of last dose of study treatment or events with start date prior to the date of first dose of study treatment whose severity worsens on or after the date of first dose of study treatment.

If an AE can't be classified as pre-treatment AE or TEAE due to missing/partial dates, it will be classified as TEAE.

The number and percentage of patients reporting each pre-treatment AE will be summarized for each treatment group and overall, by System Organ Class (SOC) and Preferred Term (PT) for SS.

All AE data will be listed by treatment group and overall. Treatment-emergence status will be flagged in the listing. In addition, corresponding listings of serious AEs (SAEs), treatment-related AEs, AEs leading to discontinuation of study treatment, AEs leading to discontinuation of study and AEs resulting in death will be produced for the SS.

The severity of all AEs is recorded as mild, moderate, or severe. If severity is missing for a TEAE, it will be considered severe only in the overall category in the summary tables.

The relationship between an AE and treatment is assessed as related, possibly related, unlikely related, or not related. A treatment-related AE is an AE considered by the investigator as related or possibly related to treatment or with missing relationship to treatment.

An overview table will summarize the number and percentage of patients with at least one of the following TEAEs, along with the number of corresponding TEAEs, where

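### An adverse event with missing severity counts as severe overall but is left out of its SOC and PT rows, so the maximum-severity tables can disagree with themselves

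*SAP*

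**What the plan says.** SAP 7.7.2 gives the rule twice. Early in the section, among the definitions: "If severity is missing for a TEAE, it will be considered severe only in the overall category in the summary tables". Later, after the list of planned AE summaries, the section repeats that an ungraded event is severe in the overall row. For the SOC and PT level it then adds: "but will not be included in the counts of patients with AEs within a SOC or PT".

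The later statement comes straight after the rule for the maximum-severity summaries: "For summaries by maximum severity, patients with multiple AEs within a particular SOC or PT will be counted under the category". The category meant is that of the worst event. The list has 13 summaries. Two of them are by maximum severity: one for all AEs and one for treatment-related AEs.

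Three other provisions bear on the point:

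- SAP 7.1 answers whether to show a Missing category: "Yes, when the number missing is greater than zero for at least one treatment group". The SAP 7.1 principles apply unless otherwise stated.
- SAP 7.7.2 handles missing relationship differently: "A treatment-related AE is an AE considered by the investigator as related or possibly related to treatment or with missing relationship to treatment".
- Protocol 8.5 plans that "the severity of TEAEs and relationship to study treatment will be summarized by SOC, PT, and treatment group", and does not mention missing severity.

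**The concern.** When severity is missing, only the grade is unknown. The event, its SOC and its PT are all known. The rule nevertheless removes the event from the SOC and PT counts while keeping it, at the worst grade, in the overall row. A reader of a maximum-severity table can then see a severe patient overall whom no SOC or PT row explains.

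The direction is fixed: leaving events out can only reduce the number of patients in a SOC or PT row. No statistical comparison of AEs is planned, so readers will judge safety from these descriptive counts. Elsewhere the SAP keeps incomplete items in the cautious group: an AE that cannot be dated becomes treatment-emergent, an AE with missing relationship becomes treatment-related, and a medication that cannot be dated becomes concomitant. Here a missing value takes an event out of a count.

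**Working it through.** The plan states no figure on this point, so there is none to reproduce. The check applies the rule as written.

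**Step 1. Where one patient lands in a maximum-severity table.**

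| Patient's AEs | Overall row | PT row of the ungraded AE | SOC row |
|---|---|---|---|
| One AE only, ungraded | Severe | Absent | Absent |
| Ungraded AE, plus a mild AE in another PT of the same SOC | Severe | Absent | Mild |
| Ungraded AE, plus a mild AE in the same PT | Severe | Mild | Mild |

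In the first line the patient is missing from both rows, and in the second from the PT row. In the third the patient is counted but graded below the overall row.

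**Step 2. Size per affected patient.** SAP 2.2 plans 174 patients randomized 1:1, so 174 / 2 = 87 per arm. This assumes that everyone is dosed as randomized, so that the Safety Set also has 87 per arm. One patient missing from a row is 1 / 87 = 1.1 percentage points. If a PT occurred in 3 patients and one of them had only an ungraded event there, the row would show 2, which is 1 / 3 = 33% too low.

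**Step 3. Illustration (assumed counts).** In an arm of 87, 10 patients have a graded AE in one SOC. A further m patients have a single AE, in that SOC, without a grade. Nobody has an AE in any other SOC. Under the rule the overall row is 10 + m and the SOC row is 10. If the ungraded events are kept, the SOC row is also 10 + m.

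| m | Overall row | SOC row, SAP rule | SOC row, events kept |
|---|---|---|---|
| 0 | 10 (11.5%) | 10 (11.5%) | 10 (11.5%) |
| 1 | 11 (12.6%) | 10 (11.5%) | 11 (12.6%) |
| 2 | 12 (13.8%) | 10 (11.5%) | 12 (13.8%) |
| 3 | 13 (14.9%) | 10 (11.5%) | 13 (14.9%) |
| 5 | 15 (17.2%) | 10 (11.5%) | 15 (17.2%) |

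The documents give no expected value for m, and at m = 0 nothing changes.

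**Step 4. Which tables are covered.** The two maximum-severity tables are certainly covered, because the sentence directly follows their counting rule. For the other SOC and PT tables the text is open. The sentences on either side each begin by naming the summaries they govern, and this one does not. The paragraph opens with a reference to all the summaries listed above it, and the early statement speaks of summary tables in general. A programmer could reasonably apply the exclusion more widely.

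**The case against.** The strongest reply is that this is only a grading rule for severity tables. Saying that an event is included as severe has meaning only in a table split by severity, and the sentence sits within a run of table-specific rules. That is the more natural reading. A reader might infer that ungraded events vanish from every SOC and PT table. The documents do not establish that: the wording permits it but does not say it. On the narrower reading the event stays in the plain incidence table and, where it applies, in the serious, related, discontinuation and death tables. On any reading it stays in the AE listings.

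The following inferences also go too far:

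- **That the rule contradicts SAP 7.1.** SAP 7.1 gives way where something else is stated, and SAP 7.7.2 states something else. It is an exception without a given reason.
- **That it contradicts Protocol 8.5.** Counting a patient once per PT prevents double counting of repeated events. It does not address missing severity.
- **That the handling of missing relationship makes it an inconsistency in law.** SAP 7.7.2 only defines a treatment-related AE as one "considered by the investigator as related or possibly related to treatment or with missing relationship to treatment". Two variables may be handled differently; the contrast shows a difference of approach and nothing more.
- **That SOC rows should add up to the overall row.** They need not, since one patient can have AEs in several SOCs. The mismatch is a patient counted overall but absent from the row where the event occurred.
- **That every ungraded event lowers a row.** It does so only when the patient has no graded AE in that row.

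Missing grades may also be rare. Protocol Appendix 1 asks the investigator to grade every AE, and Appendix 3 provides for source data verification and resolution of queries. That limits the likely size, but it does not make the rule coherent when a grade does stay missing.

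**Conclusion.** The point holds as a minor flaw in a stated rule. Followed as written, SAP 7.7.2 makes the two maximum-severity tables internally inconsistent whenever a grade is missing. A patient can be severe overall with no matching SOC or PT row, or with a row that shows a lower grade. Whether the exclusion also reaches the plain SOC and PT tables is ambiguous and should be settled in the text.

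The size is one patient per affected row for each patient with no graded AE there, about 1.1 percentage points if the Safety Set has 87 per arm. The number of such patients is unknown and may be zero. Efficacy results, alpha and power are not affected.

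**What to change.** Replace the later sentence in SAP 7.7.2 with two statements:

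1. AEs with missing severity are always counted in the SOC and PT tables that are not split by severity.
2. In the maximum-severity tables they are handled the same way at the overall, SOC and PT levels: either as severe, which extends the existing overall rule, or in a Missing row at all three levels, in line with SAP 7.1.

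Align the early statement in the same section. If the severe option is chosen, delete its restriction to the overall category. If the Missing option is chosen, rewrite it, because it now assigns such events to severe, and say where a patient with both graded and ungraded AEs is counted.

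The cost is a short SAP edit, with no new data. Under the severe option, severe counts at SOC and PT level may rise slightly, and some ungraded events that were in fact mild will be shown as severe. While the paragraph is open, correct its next sentence too: it names summaries by highest severity but describes highest relationship.

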### 7.7.3 Laboratory Evaluations

Data for the following hematology, clinical chemistry, and urinalysis analytes will be listed and summarized by treatment group and overall by visit for the SS. If data for any additional analytes are also received/recorded then these will be listed only.

Hematology	Clinical Chemistry	Urinalysis
Hematocrit	Albumin	Color and appearance
Hemoglobin	ALP	pH and specific gravity
MCH	ALT	Bilirubin
MCHC	AST	Glucose
MCV	BUN	Ketones
Platelet count	Calcium	Leukocytes
Red blood cell (RBC) count	Chloride	Nitrite
White blood cell (WBC) count	Cholesterol	Occult blood
WBC differential (% and absolute values):	Creatinine	Protein
• Basophils	GGT	Microscopic (including RBCs and WBCs)
• Eosinophils	Glucose	
• Lymphocytes	eGFR	
• Monocytes	LDH	
• Neutrophils	Phosphorus	
	Potassium	
	Sodium	
	Total Bilirubin	
	Total CO 2 (measured as bicarbonate)	
	Total Protein	
	Triglycerides	
	Uric acid	

Abbreviations: ALP = alkaline phosphatase; ALT = alanine aminotransferase; AST = aspartate aminotransferase; BUN = blood urea nitrogen; CBC = complete blood count; CO2 = carbon dioxide; eGFR = estimated glomerular filtration rate; GGT = gamma glutamyl transferase; LDH = lactate dehydrogenase; MCH = mean corpuscular hemoglobin; MCHC = mean corpuscular hemoglobin concentration; MCV = mean corpuscular volume; RBC = red blood cell; WBC = white blood cell.

All laboratory data will be reported in International System of Units (SI). Out-of-reference-range values will be flagged as high (H) or low (L) in the listings.

For analysis purposes, values preceded by a "<" or a ">" sign (i.e. those below or above the limits of quantification) will be multiplied by 0.5 and 1.5 respectively.

Results and changes from baseline (if applicable) of all laboratory parameters will be listed and summarized by treatment group and overall, for each scheduled visit using standard descriptive statistics for the SS.

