## Statistical Analysis Plan

Sponsor Name: Golden Biotechnology Corporation  
Sponsor Protocol ID: GH Covid-2-001

Covance Study ID: 000000203201

For hematology, clinical chemistry and numerical urinalysis analytes, shift tables presenting movement in and out of reference range from baseline to each scheduled post-baseline visit will be provided for each treatment group and overall for the SS.

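### SAP 7.7.3 should exempt urine specific gravity and pH from its 0.5/1.5 multiplication: any such result reported with a sign would become an impossible or implausible value in the descriptive tables

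*SAP*

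**What the plan says.** SAP 7.7.3 (Laboratory Evaluations) tabulates the hematology, chemistry and urinalysis analytes to be summarized. The urinalysis column includes "pH and specific gravity". Below the table comes one rule for results with a `<` or `>` sign, described as "i.e. those below or above the limits of quantification": for analysis they "will be multiplied by 0.5 and 1.5 respectively". No analyte or class of analyte is excepted.

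Two kinds of output follow in the same section:

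- **Descriptive summaries.** "Results and changes from baseline (if applicable) of all laboratory parameters will be listed and summarized by treatment group and overall", by scheduled visit in the Safety Set.
- **Shift tables.** The last paragraph of 7.7.3 reads: "For hematology, clinical chemistry and numerical urinalysis analytes, shift tables presenting movement in and out of reference range". It does not say whether the classification uses the result as reported or the multiplied value.

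Protocol 8.5 settles the inferential status of these data: "No formal statistical analysis of the safety data will be performed".

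**The concern.** Half the limit is a familiar stand-in for a concentration that is too low to measure, because the true value lies between zero and the limit. The SAP makes the same choice for negative viral load in 7.6.2.3. The reasoning fails for specific gravity, which is a density relative to water and varies only in the second and third decimal around 1. It fails for pH too, which is a logarithmic scale with no natural zero for urine. On these two scales a multiplier does not approximate the unseen value; it moves it far outside anything urine can show.

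What is at stake is the readability of the urinalysis tables. A few signed results could distort the mean, standard deviation, minimum or maximum and change from baseline, and a reader would have to work out that the cause was a data-handling rule.

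**Working it through.** The plan states no figure to reproduce. The check applies its rule directly.

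**Inputs**

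- Multipliers of 0.5 for `<` and 1.5 for `>`: SAP 7.7.3.
- Patients per arm: 10 + 77 = 87, from the cohort sizes in SAP 2.3, taking every patient to have a value.
- Reporting limits c: not in the documents, so assumed and shown as ranges.

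**Formula.** `<c` becomes 0.5 × c and `>c` becomes 1.5 × c.

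| Analyte | Assumed reported result | Value analysed |
|---|---|---|
| Specific gravity | `<1.000` to `<1.005` | 0.500 to 0.503 |
| Specific gravity | `>1.025` to `>1.050` | 1.538 to 1.575 |
| Urine pH | `<4.5` to `<5.5` | 2.25 to 2.75 |
| Urine pH | `>8.0` to `>9.0` | 12.0 to 13.5 |

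The specific gravity result hardly depends on the assumption: any limit near 1 gives about 0.5 or 1.5. For pH, the multiplied value leaves the 0 to 14 scale only if the limit exceeds 14 / 1.5 = 9.33 (`>9.5` would become 14.25). Below that it is implausible for urine but not off the scale.

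**One patient's change from baseline.** Take a baseline of 1.010 and a later result of `>1.030`. The true change is known only to exceed 1.030 − 1.010 = +0.020. The rule analyses 1.545 − 1.010 = +0.535. Using the limit itself gives +0.020.

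**Effect on an arm summary.** Compared with using the limit, one multiplied result shifts the arm mean by 0.5 × c / 87, upward for `>` and downward for `<`:

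- specific gravity `>1.030`: 0.515 / 87 = +0.0059
- specific gravity `<1.005`: 0.5025 / 87 = −0.0058
- pH `<5.0`: 2.5 / 87 = −0.029
- pH `>8.0`: 4.0 / 87 = +0.046

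The interval from 1.005 to 1.030 is 0.025 wide, so one such specific gravity result moves the mean by 0.0059 / 0.025, about 24% of it. The standard deviation suffers more. If the other 86 values all equalled 1.030, one multiplied result alone would give a standard deviation of 0.515 / √87 = 0.055, about twice that width. For pH the effect of a single result on the mean is small; the implausible minimum or maximum is what would show.

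**Shift tables.** Multiplication moves a value further in the direction of its sign, so a result already outside the reference range stays outside. Replacing it with the limit can do worse here. With an assumed pH range of 5.0 to 8.0, a result of `<5.0` is low; multiplied to 2.5 it is still low, but set to 5.0 it counts as normal. Shift tables therefore need the reported result with its sign, not a substituted number.

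**The case against.** The strongest objection is that the trigger is hypothetical. Neither document gives a reporting limit or says that pH or specific gravity will arrive with a sign. If they never do, nothing happens. Even if they do, the tables are descriptive, the same rule applies to both blinded arms, and out-of-range results are flagged in the listings. All of that stands, and it keeps the point small. It does not remove it: the plan cannot control how the laboratories report, and a prespecified rule should not give impossible values when it is triggered.

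A reader might infer more than the documents support:

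- **False eGFR changes or a masked renal signal.** `>60` would become 90, so a move from 58 to `>60` would be analysed as +32. But the true change is known only to exceed +2. It could be near +2 or near +32, and the documents cannot say which substitute is closer. eGFR is a ratio-scale quantity, so multiplication is not meaningless for it, and creatinine and BUN are summarized separately.
- **Corrupted shift tables.** Misclassification under the multiplication needs a reporting limit inside the reference range, which the documents do not show.
- **Effects on eligibility.** The multiplication is confined to analysis. Eligibility is judged on screening results as the laboratory reports them (Protocol 7.2.3).
- **A fault in all `>` values.** No defect is shown for concentration analytes above the measuring range. Changing them would be a preference.

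**Conclusion.** The point holds in a narrow, conditional form. SAP 7.7.3 exempts no analyte from the multiplication, and urine pH and specific gravity are in its scope. Should either be reported with a sign, specific gravity takes values of about 0.5 or 1.5 whatever the exact limit, and pH takes values such as 2.5 or 12.0 under the assumed limits. These would enter descriptive means and changes from baseline. The pH values are implausible for urine rather than impossible on the scale.

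The conclusion about the rule's wording rests on the SAP text alone. The sizes rest on assumed reporting limits and, for arm means, on 87 evaluable patients. How many results would be affected cannot be estimated from the documents and may be none. No efficacy result, eligibility decision or formal test is involved, so this is a minor correction worth making because it is nearly free.

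**What to change.** Add to SAP 7.7.3 that urine pH and specific gravity are exempt from the multiplication, and that a signed result for either enters the descriptive summaries at the reporting limit itself. Add also that shift tables classify the result as reported, including its sign, and not a substituted value. If a limit lies inside the reference range, the sign may not settle the category, and the programming specification should say how such a result is shown.

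Leave the rule as it is for eGFR and for concentration analytes, in both directions.

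The cost is one or two sentences in the SAP and a small programming change. Using the limit understates how far beyond it the true value lies, which is acceptable in a descriptive table on these narrow scales. No new data are needed, and no other analysis changes.
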